8.3. Procedures and Schedule of Assessments

The study will be conducted as outlined in the following sections. [Table 2](#) summarizes the study assessments at each study visit for patients enrolled in this study, followed by an overview of assessments by visit in [Sections 8.3.1-8.3.8](#). Further details of the assessments are provided in the Study Operations Manual.

Table 2: Schedule of Events (Subject Visit Schedule)

Visit	S1 ^{1,2}	S2	S3	T1	T2	T3/phone	T4	T5/EOS ³
Week	Wk -5	Wk -4	Wk -1	Wk 0	Wk 4	Wk 8	Wk 12	Wk 24
Procedure	Day -63 to -29	Day -28 ±3	Day -7±3	Day 1	Day 29±3	Day 57±3	Day 85±3	Day 169 ±7
Informed Consent	X							
Enrollment Criteria	X							
Demographics	X							
Medical History	X							
Statin Intolerance Status Determination	X							
Concomitant Medications	X	X	X	X	X	X	X	X
Adverse Event Recording		X	X	X	X	X	X	X
Physical Exam		X						X
Weight ⁴	X			X			X	X
Height/BMI	X							
12-Lead ECG ⁵			X					X
Vital Signs ⁶	X	X	X	X	X		X	X
Serology ⁷	X							
Serum Pregnancy ⁸	X							
Urine Pregnancy ⁹				X				
TSH	X							
Clinical Safety Labs ¹⁰	X		X	X	X		X	X
Basic Fasting Lipids ¹¹	X		X	X	X		X	X

Table 2: Schedule of Events (Subject Visit Schedule)

Visit	S1 ^{1,2}	S2	S3	T1	T2	T3/phone	T4	T5/EOS ³
Week	Wk -5	Wk -4	Wk -1	Wk 0	Wk 4	Wk 8	Wk 12	Wk 24
Procedure	Day -63 to -29	Day -28 ±3	Day -7±3	Day 1	Day 29±3	Day 57±3	Day 85±3	Day 169 ±7
HbA _{1c}	X			X			X	X
PK sample					X		X	X
apoB				X			X	X
hs-CRP				X			X	X
Diet and exercise counseling ¹²	X	X	X	X	X	X	X	
Establish Patient Eligibility		X		X				
Randomization				X				
IWRS Contact ¹³	X	X		X			X	X
Single-blind Drug Dispensing		X						
Double-blind Drug Dispensing				X			X	
Drug Return/Compliance			X	X	X		X	X

NOTE: For patients who withdraw from study drug treatment, but consent to be followed for safety assessments and return to clinic for these visits, the visits will occur according to the protocol schedule. Safety assessments should include clinical safety and basic lipid laboratories (except for apoB and hs-CRP), adverse events (AEs), physical examination (PE), vital signs, and electrocardiograms (ECGs).

¹ An optional fasting (minimum of 10 hours) TG assessment MAY be completed between Visits S1 and S2 (prior to starting single-blind medication) if patient fails to meet TG criterion at Visit S1. The repeat value will be used to determine eligibility.

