8.3.7. Treatment Week 12 (Visit T4; Day 85 ±3 days)

Patients will undergo the following assessments and procedures at Week 12 (Visit T4):

1. Concomitant medication review (ongoing)
2. Assess AEs, SAEs, and potential clinical endpoints (ongoing)
3. Weight
4. Vital signs
5. Central clinical laboratory evaluations:
 - Hematology, blood chemistry, and urinalysis
 - apoB
 - hs-CRP
 - HbA_{1C}
 - Basic fasting lipids (TC, calculated LDL-C, HDL-C, non-HDL-C, and TG)
 - PK Sample before dose

6. Diet and exercise counseling
7. Return of study drug; assessment and recording of dosing adherence
8. IWRS contact to obtain new MED ID numbers for double-blind study drug
9. Dispense double-blind study drug and provide dosing instruction

Note: If the patient discontinues at any scheduled visit after T1, or between study visits, please proceed to [Section 8.4.1](#) for detailed instructions.

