8.4. Early Withdrawal from Study or Treatment

Patients who withdraw from study drug prior to Week 24 (Visit T5) for any reason will be asked to continue to be followed for safety assessments, including basic fasting lipids, at clinic visit following the protocol-specified visit schedule (see [Section 8.3](#)).

Patients who temporarily withdraw from study drug prior to Week 24 (Visit T5) for any reason may restart study drug providing that 1) the patient and the investigator are in agreement regarding this course of action, 2) the patient has been off of study drug for 4 weeks or less; and 3) study drug can be started as soon as possible. For cases where the patient has been off of study drug for more than 4 weeks, the investigator must contact the medical monitor for approval prior to restarting study drug.

Patients who do not wish to continue to return to the clinic for safety assessments will be asked to participate in phone calls from the site at protocol-specified visits (see [Section 8.3](#)), or at a minimum at 24 weeks, to collect information on AEs, concomitant medications, and current health status.

The patient's decision to participate in the clinical study is voluntary. Patients may refuse to continue in the study and/or withdraw from participation in this study at any time, for any reason, specified or unspecified, and without penalty or loss of benefits to which the patient is otherwise entitled.

It is the right and duty of the Investigator to interrupt the treatment of any patient whose health or well-being may be threatened by continuation in this study. Such patients should be withdrawn from the study and should not be continued under a modified regimen.

Patients who are withdrawn from the study may not re-enter. The reasons for withdrawal from this study or treatment may include:

- Patient's withdrawal of consent
- Failure to comply with the protocol
- Lost to follow-up
- Illness, condition, or procedural complication (including AEs) affecting the patient's ability to participate or requiring prohibited medication
- The Sponsor or Investigator terminates the study
- In the Investigator's judgment, it is deemed in the best interest of the patient to discontinue his/her participation in the study
- Any other reason

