9.2. Clinical Efficacy Laboratory Tests

Blood draws for efficacy (not safety) must meet the criteria below. If these criteria have not been met, efficacy blood samples will NOT be collected. **If these criteria can be met by rescheduling the clinic visit (within 3 days), efficacy blood samples will be collected at the rescheduled clinic visit only.**

- Blood samples will be drawn after a minimum 10-hour fast (water is allowed), and
- Patients will be in a seated position during the blood collection. Clinical laboratory parameters and tests will include those listed in [Table 3](#). Collection schedule and instructions are provided in the Clinical Laboratory Manual. A description of the sample collection, storage, and shipping as well as monitoring and management of abnormal laboratories are described in [Section 10.1.6](#).

When ECG, vital signs, and laboratory samples are to be collected at the same time point, ECG and vital sign measurements will precede laboratory sample collection.

Table 3: Clinical Efficacy Laboratory Tests

Clinical Laboratory Test	Clinical Laboratory Test
Basic Lipid Parameters 
• Total cholesterol (TC)• low-density lipoprotein cholesterol (LDL-C) and non-HDL-C 	Other Parameters 
• High-sensitivity C-reactive protein (hs-CRP)• Apolipoprotein B (apoB)

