11.5. Primary Endpoint Analysis

The primary efficacy endpoint is the percent change from baseline to Week 12 in LDL-C. Baseline is defined as the mean of the values from Week -1 (Visit S3) and predose Day 1/Week 0 (Visit T1).

The primary efficacy endpoint will be analyzed using analysis of covariance (ANCOVA), with treatment group and patient type (primary prevention; secondary prevention) as factors and

baseline LDL-C as a covariate. The ANCOVA will be performed using the FAS, with patients included in their randomized treatment group regardless of the treatment they actually received. The details of the ANCOVA model and options to account for unequal variances and group size will be described in the SAP.

Missing data for the primary endpoint will be imputed using a multiple imputation method that accounts for treatment adherence. A pattern mixture model (PMM) will be used to specify different imputation strategies depending on whether the patient is still on study treatment. Patients with missing LDL-C data at Week 12 who are no longer taking study treatment can be assumed no longer to be benefitting from study medication, and their missing value(s) can be assumed to be similar to those from placebo patients. In this instance, it is reasonable to impute LDL-C values in a model including placebo patients' data only. Patients with missing LDL-C data at Week 12 who are still taking study treatment can be assumed to continue to benefit from study medication, and their missing value(s) can be assumed to be similar to those who remain on study treatment and have data. In this instance, it is reasonable to impute LDL-C values based on the observed values in their randomized treatment group at Week 12. Details for the PMM will be described in the SAP.

To account for uncertainty, missing values will be imputed using multiple imputation. Imputed datasets will be analyzed using an ANCOVA model with the treatment and patient type (primary prevention; secondary prevention) as factors and baseline LDL-C as a covariate. Approximately 200 imputed datasets will be created, with results from the analysis of each imputed dataset combined using Rubin's method. For each type of ANCOVA (observed case; imputation via PMM), the least squares mean (LSM) and standard error (SE) will be provided for both treatment groups, along with the placebo-corrected LSM, its 95% confidence interval (CI) and associated p-value.

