**18.1.3. MISSING DATA METHODS FOR PRIMARY EFFICACY VARIABLE**

For the primary endpoint of percent change from baseline to Week 12 in LDL-C values, a pattern mixture model (PMM) will be used to specify different imputation strategies depending on whether the patient is still on study treatment. Patients with missing lipid data at Week 12 who are no longer taking study treatment (defined by date of last dose of study medication is < Week 12 lab assessment date -7) can be assumed to no longer be benefitting from study medication, and their missing value(s) can be assumed to be similar to those in placebo group who remained on study and have data. To account for uncertainty, missing values will be imputed using multiple imputation via a regression based model including stratification and baseline data from placebo subjects only. In this imputation model, treatment group will not be included as a factor.

Patients with missing lipid data at Week 12 who are still taking study treatment (date of last dose of study medication is ≥ Week 12 lab assessment date -7) can be assumed to continue to benefit from study medication, and their missing value(s) can be assumed to be similar to those who remain on study treatment and have data and as a result, lipid values will be imputed based on the observed values in their randomized treatment group at Week 12. To account for uncertainty, missing values will be imputed using multiple imputation via a regression based model including treatment, stratification and baseline value.

Imputed datasets will be analyzed using the same ANCOVA model with treatment and stratification as factors and baseline LDL-C as a covariate described in [section 18.1.2](#). Approximately 200 imputed datasets will be created, with results from the analysis of each imputed dataset combined using Rubin’s method. The least squares mean (LSM) and standard error (SE) will be provided for both treatment groups, along with the placebo-corrected LSM, its 95% confidence interval (CI) and associated p-value. To account for possibility of unequal variances between the groups, the ANCOVA model will be implemented within mixed model framework where <repeated/group=> option will be used to allow separate estimation of residual variance between the groups.

Further information on the multiple imputation method is presented in [Appendix 4](#).

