**APPENDIX 4. DETAILS OF MULTIPLE IMPUTATION METHOD**

Missing Week 12 values will be imputed based on baseline values. The following table details the possible cohorts and which cohorts will be used for imputation. Missing Week 24 values will be imputed in the same way.

	Treatment	Week 12 Value	On Treatment at Week 12	Imputation Cohort(s)
1	Placebo	Missing	Yes	Cohort 5: Placebo patients with non-missing Week 12
2	BA	Missing	Yes	Cohorts 6 and 8 BA patients with non-missing Week 12
3	placebo	Missing	No	Cohort 5: Placebo patients with non-missing Week 12
4	BA	Missing	No	Cohorts 5 and 7 Placebo patients with non-missing Week 12 and not on treatment
5	placebo	Non-missing	Yes	
6	BA	Non-missing	Yes	
7	placebo	Non-missing	No	
8	BA	Non-missing	No	

Imputation code for Cohorts 1-3.

```
proc mi;
where cohort in(1,2,3,5,6,8);
class trt01pn strata;
monotone regression;
var trt01pn strata base aval;
run;
```

Imputation code for Cohort 4.

```
proc mi;
where cohort in(4,5,7);
class strata;
monotone regression;
var base strata aval;
run;
```

[figure not shown]
Version Number: 1.7  
 Version Date: 21Mar2018

Two hundred imputed datasets will be created, with results from the analysis of each imputed dataset (ANCOVA) combined using Rubin’s method.

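### Does the imputation rule break down for patients with no Week 12 blood draw, who have no Week 12 lab date to compare with their last dose?

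*SAP*

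**What the plan says.** SAP 18.1.3 uses a pattern mixture model that sorts patients with missing Week 12 lipids into two classes. Those no longer on study drug are "defined by date of last dose of study medication is < Week 12 lab assessment date -7"; their values are imputed from placebo data. Those still on study drug are the ones for whom "date of last dose of study medication is ≥ Week 12 lab assessment date -7"; their values are imputed from their own randomized arm.

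Appendix 4 turns this into a Yes/No column for treatment status at Week 12 and places every patient with a missing value in one of cohorts 1 to 4. It adds: "Missing Week 24 values will be imputed in the same way".

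Protocol 11.5 gives the reasoning without a date. Patients "who are no longer taking study treatment can be assumed no longer to be benefitting from study medication", while those still taking it are assumed to keep the benefit. Details are left to the SAP.

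Several protocol provisions bear on who lacks a Week 12 date:

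- Section 8.4: "Patients who do not wish to continue to return to the clinic for safety assessments will be asked to participate in phone calls".
- Section 9.2, on fasting and posture for efficacy draws: "If these criteria have not been met, efficacy blood samples will NOT be collected".
- The note to Table 2 in 8.3: patients off drug who still attend have safety and basic lipid samples taken, but not apoB or hs-CRP.
- Section 8.3.7 sets the Week 12 visit at Day 85, with a tolerance of 3 days.

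**The concern.** The rule is needed only when the Week 12 value is missing, yet it refers to a date that a patient with no Week 12 draw does not have. Phone-only follow-up in Protocol 8.4 makes such patients foreseeable. The class decides whether a missing bempedoic acid value is imputed with or without drug benefit in the primary analysis, and again for Week 24 LDL-C, the first key secondary test.

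Three mishandlings can be imagined:

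- The comparison is coded literally in SAS, where a missing date sorts below any real one. Every such dropout is then classed as on treatment and imputed from the active arm.
- The patient is put in no cohort and is not imputed.
- All such patients are set to off, including some who were still taking drug and only missed the visit.

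The first two would overstate the effect and the third would understate it. At stake are the size of the primary estimate and its reproducibility.

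**Working it through.** **Who is affected.** Where any Week 12 sample was drawn, a lab date exists and the rule works. That covers visits with safety samples but no efficacy sample, and off-drug attenders without apoB and hs-CRP. In the placebo arm the class makes no difference, because Appendix 4 gives cohorts 1 and 3 the same donors (cohort 5). What remains is bempedoic acid patients with no Week 12 draw at all.

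**Which of them are ambiguous.** The last dose date is on the End of Treatment page (SAP 17.1), so only the reference day is open. Cut-off = reference day − 7, and a patient is off treatment if the last dose falls before it.

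| Reference day | Source | Cut-off |
|---|---|---|
| 85 | Protocol 8.3.7 target | 78 |
| 82 | target − 3 | 75 |
| 88 | target + 3 | 81 |
| 72 | lower edge of SAP window | 65 |
| 127 | upper edge of SAP window | 120 |

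The visit labels of the window table in SAP 6.4 are not legible. The window 72 to 127 is taken as Week 12 because it is seventh of eight and its limits fit the midpoints between visit days: (57 + 85)/2 = 71 and (85 + 169)/2 = 127.

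Under every candidate, a last dose before Day 65 is off and one on or after Day 120 is on. Only Days 65 to 119 can change class. If the reference day is kept within the protocol's own visit tolerance, this shrinks to Days 75 to 80. For Week 24 the Day 169 target gives 169 − 7 = 162.

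**Size per patient.** The documents give 200 and 100 patients per arm but no legible effect, SD or dropout rate. Assume an on-drug versus off-drug difference D of 15 to 25 percentage points. Moving m patients between imputation models shifts the bempedoic acid mean by (m/200) × D:

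- m = 1: 0.075 to 0.125 points
- m = 2: 0.15 to 0.25
- m = 5: 0.375 to 0.625
- m = 10: 0.75 to 1.25

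With an assumed SD of 20, the standard error of the difference is 20 × √(1/200 + 1/100) = 2.45 points.

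**A deliberate worst case.** A simulation made every missing bempedoic acid patient an off-drug patient with no draw and then misclassified all of them (600 trials per scenario, 20 imputations, SD 20). With a true effect of −20 and 5% missing:

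- intended rule: −18.94
- all classed as on treatment: −19.95
- left unimputed: −19.95

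The shift of 1.01 matches 0.05 × 20 = 1.0. With no true effect the shift was at most 0.02 points, and rejection under the first mishandling was 3.8% to 5.7% (simulation error about 0.9%). Power was at least 99.8% in every scenario with an effect. These runs measure a programming fault applied to everyone, not the ambiguity in Days 65 to 119. They also leave out the cohort 8 donors (off-drug bempedoic acid patients with observed values), whom Appendix 4 includes when imputing cohort 2 and who would be expected to reduce the shift.

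**The case for a change.** The strongest case for acting is that the SAP states a definition, and Protocol 11.1 lets the SAP override the protocol on analysis, so appeal to the protocol's intent is not enough. The affected patients are the very dropouts that placebo-based imputation was designed for. The SAP supplies fallbacks elsewhere: randomization date for a missing first dose in 6.1, and partial dates in Appendix 2. One sentence would have closed the gap.

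Part of this stands. The readable text of 18.1.3 and Appendix 4 does not name the reference date, and an unguarded comparison in SAS would give the wrong class.

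The rest does not carry. SAP 18.1.3 itself opens each class with whether the patient is still taking study treatment; the date comparison only implements that. Appendix 4 assigns every missing patient a Yes or No, so leaving someone unimputed contradicts it. So does recording an early dropout as on treatment at Week 12. These would be departures from the plan, and nothing in the documents suggests they happened. Absence from the plan is not shown either: SAP 6.3 covers retests, unscheduled visits and early termination data and 6.4 covers windowing, and most of that text is unreadable in the public copy.

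**Conclusion.** This is missing detail that an analyst fills sensibly, most naturally with first dose date + 84 (Day 85). It gives no ground to alter the plan. The class is open only for bempedoic acid patients who had no Week 12 draw and took their last dose between about Day 65 and Day 119. Few are likely, because patients off drug are asked to keep attending with fasting lipids (Protocol 8.4), though the documents give no count.

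Each such patient is worth at most about 0.125 points if the drug effect is 15 to 25 points. Five of them would move the estimate by 0.375 to 0.625 points, about a quarter of the 2.45-point standard error at most. The significance test is essentially unaffected.

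The completer, on-treatment and observed-data analyses in SAP 18.2.3 use no imputation and so do not need the flag. In the worst-case simulation, wholesale misclassification made the primary result coincide with the observed-data result, so that planned comparison would help expose it.

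The SAP addendum reports that the planned analysis was completed and the study unblinded. Choosing a new cut-off now and replacing the primary result would be a post-hoc change with nothing to gain.

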**18.2. SECONDARY EFFICACY**

The secondary efficacy analyses will be performed for the full analysis set (FAS).

[REDACTED]

Version Number: 1.7  
 Version Date: 21Mar2018

[REDACTED]

**18.2.1. KEY SECONDARY EFFICACY VARIABLES & DERIVATIONS**

The key secondary endpoints, which are included in the hierarchical analysis described in [Section 7.5](#), are:

- percent change from baseline to Week 24 in LDL-C
- percent change from baseline to Week 12 in non-HDL-C
- percent change from baseline to Week 12 in TC
- percent change from baseline to Week 12 in apoB
- percent change from baseline to Week 12 in hsCRP.

Key secondary endpoints of LDL-C, non-HDL-C, TC, and apoB will be analyzed using the same ANCOVA model described in 18.1.2.

Similar to the primary endpoint, missing data will be imputed using multiple imputation method as described in 18.1.3.

For hsCRP, a non-parametric (Wilcoxon rank-sum test) analysis with Hodges-Lehmann estimates and confidence interval will be performed because based on historical knowledge, publication precedence (Brendan etc., 2006) and recent data available, hsCRP is known to be skewed by extreme values and have non-normal distribution.

Graphic presentations (mean+/-SE) or median (IQR) for efficacy parameters will be provided.

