In this hierarchical testing structure, each hypothesis is tested at a significance level of 0.05, two-sided. Statistical significance at each step is required in order to test the next hypothesis. If the primary endpoint meets the criteria for statistical significance, then the percent change from baseline to Week 24 in LDL-C will be tested; and so forth.

For the remaining secondary efficacy endpoints and the tertiary efficacy endpoints, a significance level of 0.05 will be used; given the large number of remaining endpoints, the p-values for those endpoints will be considered descriptive.

Percent change from baseline to Week 24 in LDL-C; change from baseline to Weeks 12 and 24 in LDL-C; percent change from baseline to Weeks 12 [REDACTED] in [REDACTED] non-HDL-C, [REDACTED] TC, apoB, and

hs-CRP will each be analyzed using ANCOVA with treatment group and patient type (primary prevention; secondary prevention) as factors and the relevant baseline as a covariate. Baseline for [REDACTED] non-HDL-C, [REDACTED] and TC will be defined as the mean of the lipid values from Week -1 (Visit S3) and predose Day 1/Week 0 (Visit T1). Baseline for apoB and hs-CRP will be defined as the predose Day 1/Week 0 (Visit T1) value. Each ANCOVA will be performed using the FAS, with patients included in their randomized treatment group regardless of the treatment they actually received. Only observed case data will be included in each analysis (no imputation will be performed for missing data). For each lipid parameter and analysis time point, the LSM and SE will be provided for both treatment groups, along with the placebo-corrected LSM, its 95% CI and associated p-value.

For all continuous efficacy endpoints (percent change from baseline in LDL-C, [REDACTED] non-HDL-C, TC, [REDACTED] apoB, and hs-CRP; change from baseline in LDL-C; to Weeks 12 and 24, as appropriate), the ANCOVA assumption of normality will be assessed. If non-normality of the data is found at any time point for any parameter, either the data will be transformed so that it is normally distributed or a nonparametric test will be used instead of the planned ANCOVA.

Additional Post-randomization Adjunctive Triglyceride-lowering Therapy:

The number and percent of patients in each treatment group requiring additional (post-randomization) TG-lowering therapy will be summarized. The medications will be summarized by treatment group.

Safety Analyses

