Each ANCOVA will be performed using the FAS, with patients included in their randomized treatment group regardless of the treatment they actually received. Same imputation method described for the primary endpoint will be used for those secondary endpoints included in the step-down procedure, while only observed data analysis will be used for other secondary and tertiary endpoints. For each lipid parameter and analysis time point, the LSM and SE will be provided for both treatment groups, along with the placebo-corrected LSM, its 95% CI and associated p-value.

The ANCOVA assumption of normality will be assessed. If severe non-normality of the data is found at any time point for any parameter, either the data will be transformed so that it is normally distributed or a nonparametric test will be considered instead of the planned ANCOVA.

Finally, the number and percent of patients in each treatment group requiring additional (post-randomization) TG-lowering therapy will be summarized. The medications will be summarized by treatment group.

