18.2.3.4. Observed Data Analysis

The observed case data with no imputation for missing data will be used in sensitivity analyses for primary and key secondary endpoints.

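### If hsCRP is imputed as SAP 18.2.1 most naturally says, Appendix 4's untransformed regression draws impossible negative values, shifts the Hodges-Lehmann estimate and costs the Wilcoxon test some power

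*SAP*

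**What the plan says.** hsCRP closes the step-down sequence in SAP 7.5, tested at two-sided 0.05.

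**Whether it is imputed.** SAP 18.2.1 lists hsCRP among the key secondary endpoints, assigns the ANCOVA to the other four, and then says that "missing data will be imputed using multiple imputation method as described in 18.1.3". A separate hsCRP paragraph follows. Protocol 11.6 is broader: "Same imputation method described for the primary endpoint will be used for those secondary endpoints included in the step-down procedure". SAP 18.2.3.4 treats the unimputed version as secondary: "The observed case data with no imputation for missing data will be used in sensitivity analyses for primary and key secondary endpoints". Against this, the protocol synopsis says of the secondary endpoints: "Only observed case data will be included in each analysis (no imputation will be performed for missing data". Protocol 11.1 lets the SAP prevail over the protocol on data analysis.

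**How it would be imputed.** For patients off drug with missing data, SAP 18.1.3 states the aim: "their missing value(s) can be assumed to be similar to those in placebo group who remained on study and have data". Appendix 4 implements this with PROC MI monotone regression. For off-drug bempedoic acid patients the variable list is "var base strata aval", fitted on placebo donors. No transformation, minimum or maximum is shown.

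**How it would be tested.** Wilcoxon rank-sum with a Hodges-Lehmann estimate and interval, because "hsCRP is known to be skewed by extreme values and have non-normal distribution".

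**Who would be missing.** The note to protocol Table 2, on patients who stop drug but keep attending, reads: "Safety assessments should include clinical safety and basic lipid laboratories (except for apoB and hs-CRP").

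**The concern.** The SAP gives up normality for the hsCRP test but, on the natural reading, keeps it for the imputation. A normal regression on raw values of a skewed, strictly positive variable has a residual SD comparable to its mean. Some draws then fall below zero, which means a percent change below -100%. Because hsCRP is not scheduled after drug is stopped, missing values are likely to concentrate in the off-drug patients whom 18.1.3 wants to resemble placebo.

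At stake are the plausibility of the data behind a confirmatory step, the size of the reported hsCRP reduction, and the power of step 6. No other endpoint is affected.

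**Working it through.** The documents give no hsCRP SD, effect or missing rate, so there is no planned figure to reproduce.

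**Inputs from the documents:** 200 versus 100 patients; two-sided 0.05; Appendix 4 cohorts and predictors; Wilcoxon and Hodges-Lehmann.

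**Assumed:** lognormal hsCRP; log SD s = 0.8 to 1.2; log-scale correlation of baseline and Week 12 ρ = 0.4 to 0.8; on-drug ratio 0.75, 0.65 or 0.55; 5 to 15% missing, 70% of it off drug (0 to 100% also tried). Central case: s = 1.0, ρ = 0.6.

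**Step 1: negative draws by hand.** With the raw mean set to 1, the SD is √(e^(s²) − 1), the raw-scale correlation is r = (e^(ρs²) − 1)/(e^(s²) − 1), and the residual SD is SD × √(1 − r²). At average baseline, P(draw < 0) = Φ(−1/residual SD).

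| s (ρ = 0.6) | SD | r | residual SD | P(draw < 0) |
|---|---|---|---|---|
| 0.8 | 0.947 | 0.522 | 0.807 | Φ(−1.238) = 11% |
| 1.0 | 1.311 | 0.478 | 1.151 | Φ(−0.869) = 19% |
| 1.2 | 1.795 | 0.426 | 1.623 | Φ(−0.616) = 27% |

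Full simulation of the Appendix 4 logic gave 10 to 26% over the grid and 19% centrally. At 10% missing, 30 of 300 values are imputed, so 30 × 0.19 ≈ 6 are impossible in each imputed dataset.

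**Step 2: Hodges-Lehmann estimate.** Off-drug bempedoic acid patients were generated with no drug effect, so the complete data represent the 18.1.3 target. Raw and log imputation were compared on the same trials (ratio 0.75, 10% missing). Run A used 4,000 trials with 20 imputations. Run B, on the same central assumptions, used 400 trials with 8 imputations, omitted strata, and also recorded θ = P(bempedoic acid change > placebo change), where 0.5 means no difference.

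| Analysis | Hodges-Lehmann, A | Hodges-Lehmann, B | θ, B |
|---|---|---|---|
| Observed cases | −21.2 | −20.8 | 0.4117 |
| Complete data (target) | −19.8 | −19.5 | 0.4181 |
| Raw imputation (Appendix 4) | −21.0 | −20.6 | 0.4198 |
| Log imputation | −19.9 | −19.6 | 0.4178 |

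In run A, raw imputation overstates the reduction by 21.0 − 19.8 = 1.2 points. It keeps only (21.2 − 21.0)/(21.2 − 19.8) = 0.2/1.4 ≈ 14% of the intended shift; log imputation keeps about 90%. At 10% missing the overstatement is 1.2, 1.6 and 2.0 points for ratios 0.75, 0.65 and 0.55, against at most 0.1 with log imputation. The share kept depends on the assumptions: with all missing patients off drug, raw keeps 33 to 34%. A separate simulation (ratio 0.78, s from 0.6 to 1.2, equal missingness in both arms) found 28 to 80% of the shift undone.

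**Step 3: Wilcoxon test.** In run B the intended move in θ is 0.4181 − 0.4117 = 0.0064. Raw imputation moves it by 0.4198 − 0.4117 = 0.0081, or 127% of the target, slightly toward the null. In the separate simulation, imputed off-drug patients had probability 0.500 to 0.508 of a lower change than placebo. The normal model draws too low at one end and too high at the other, and in ranks these offset. The over-spread draws do, however, place fewer differences between zero and the drug effect, so they pull the Hodges-Lehmann estimate toward zero less than true placebo-like values would.

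**Step 4: power and type I error at 10% missing, central case.** Power lost, raw versus log, in percentage points:

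| Ratio | Rubin on z | Median p | Rubin on Hodges-Lehmann |
|---|---|---|---|
| 0.75 | 4.4 | 2.4 | 4.3 |
| 0.65 | 1.4 | 0.4 | 1.8 |
| 0.55 | at most 0.4 | at most 0.4 | at most 0.4 |

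With no drug effect (s = 0.8 to 1.2), rejection was 2.3 to 4.8% with raw and 2.9 to 5.3% with log imputation across the rules (complete data 5.6%, Monte Carlo SE 0.5).

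**The case against.** **hsCRP may not be imputed at all.** In 18.2.1 the imputation sentence comes before the hsCRP paragraph; 18.1.3 speaks of lipid data and describes Rubin's method for the ANCOVA only; protocol Table 3 files hs-CRP under other parameters; the synopsis says no imputation. If so, the problem does not arise. This stands as a condition on the point. It does not remove it, since protocol 11.6 covers every step-down secondary endpoint and SAP 18.2.3.4 makes the unimputed analysis a sensitivity analysis.

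**The test itself is not compromised.** A reader might infer that negative draws, ranked ahead of every observed patient, largely undo the placebo-like handling and tilt step 6 toward the drug. The plan does not support that. SAP 7.5 gates on statistical significance and 18.2.1 makes the test a Wilcoxon. On the rank scale the imputed off-drug patients stay placebo-like, power falls rather than rises, and type I error is not inflated. The loss of the placebo-based shift concerns the Hodges-Lehmann estimate only.

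**Safeguards exist.** SAP 18.2.3.1, 18.2.3.3 and 18.2.3.4 plan unimputed analyses. They help, but in run A the observed-case estimate (−21.2) lay next to the raw-imputed one (−21.0), so agreement between them would not show that the placebo-based shift had been lost.

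**The visible plan may be incomplete.** SAP version 1.7 added an hsCRP analysis, and 18.3.4 is blank in the public copy. The point concerns only the confirmatory analysis that can be read.

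**Conclusion.** The point holds, conditionally and at modest size. If hsCRP is imputed by Appendix 4 as written, roughly 10 to 25% of imputed values are negative for log SD 0.8 to 1.2. The Hodges-Lehmann reduction is overstated by about 1 to 2 percentage points at 10% missing, and the Wilcoxon test loses about 0 to 5 points of power in central cases, depending on the effect and the pooling rule.

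That imputation is intended is the more natural reading, not a certainty. Every magnitude rests on assumed distributions, effects and missing rates. The choice of Wilcoxon and Hodges-Lehmann is sound. The change is worth making because a confirmatory analysis should not contain impossible values and the remedy is cheap; nothing here suggests a false-positive risk.

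**What to change.** State in SAP 18.2.1 whether hsCRP is imputed. If it is, impute ln(Week 12 hsCRP) from ln(baseline hsCRP) and stratum with the same Appendix 4 cohorts (keeping treatment in the model where Appendix 4 has it), exponentiate, compute percent change, and apply the prespecified Wilcoxon and Hodges-Lehmann analysis. Give a value for below-quantification results before logs are taken; SAP 19.4 already converts them to the limit for quantitative summaries.

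Two accompanying clarifications: name, before unblinding, one rule for pooling the rank-test p-value and the Hodges-Lehmann estimate and interval, and say which governs step 6 if they disagree; and align the synopsis sentence with protocol 11.6 and the SAP.

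The cost is SAP wording and a few lines of code. No new data are needed.
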